9.2 Exclusion Criteria

Treatment Cohort

Subjects who meet any of the following exclusion criteria will NOT be eligible for this study.

1. History of any comorbidity that, in the opinion of the investigator, might confound the results of the study or pose an additional risk in administering study drug to the subject. For example:

History of cirrhosis with portal hypertension, and/or history of risk factors for Torsade de Pointes (e.g., familial long QT syndrome, hypokalemia, heart failure, left ventricular hypertrophy, bradycardia, myocardial infarction, cardiomyopathy, history of arrhythmia [ventricular and atrial fibrillation], obesity, acute neurologic events [subarachnoid hemorrhage, intracranial hemorrhage, cerebrovascular accident, and intracranial trauma], and autonomic neuropathy)

2. Pregnant and nursing females. Females of childbearing potential must have a negative urine pregnancy test at the Day 1 Visit (and the Returning Visit for subjects who re-enroll) and before receiving the first dose of study drug.
3. Sexually active subjects of reproductive potential who are not willing to follow the contraception requirements outlined in [Section 11.8.8.1](#).
4. History of drug intolerance in the parent study or other qualified Vertex study that would pose an additional risk to the subject in the opinion of investigator or Vertex. Examples of subjects who may not be eligible for the Treatment Cohort include the following:
 - Subjects with a history of allergy or hypersensitivity to the study drug
 - Liver function test (LFT) abnormality during study drug treatment in the parent study or other qualified Vertex study that required permanent study drug discontinuation
 - ECG abnormality (e.g., persistent QTc >450 msec) during study drug treatment in the parent study or other qualified Vertex study that required permanent study drug discontinuation
 - Other severe or life-threatening reactions to the study drug in the parent study or other qualified Vertex study.
5. History of poor compliance with study drug and/or procedures in the parent study or other qualified Vertex study as deemed by the investigator.
6. Participation in an investigational drug trial (other than Studies VX13-661-103, VX14-661-106, VX14-661-107, VX14-661-108, VX14-661-109, VX14-661-111, other Vertex studies investigating VX-661 in combination with ivacaftor, or other qualified Vertex study) or use of a commercially available CFTR modulator (e.g., Kalydeco) as defined in [Table 9-1](#). NOTE: participation in a noninterventional study (including observational studies, registry studies, and studies requiring blood collections without administration of study drug), and screening for other qualified Vertex studies is permitted.

7. Subjects who are enrolled in a qualified Vertex parent study with more than 1 blinded-treatment periods but who have not completed treatment in all blinded-treatment periods are not eligible to enroll in the Treatment Cohort but may be eligible to enroll in the Observational Cohort if inclusion criteria are met.
8. Previous re-enrollment in the Treatment Cohort of Study VX14-661-110, after participating in other qualified Vertex studies.

9.3 Study Restrictions (Treatment Cohort)

For subjects enrolled in the Treatment Cohort, prohibited medications and certain foods are not allowed in this study while subjects are receiving study drug (Table 9-1). Both VX-661 and ivacaftor are metabolized predominantly via the hepatic enzymatic pathway utilizing CYP3A4. Co-administration of VX-661 and ivacaftor with moderate and strong CYP3A inducers such as rifampin, phenobarbital, carbamazepine, phenytoin, and St. John's wort (*Hypericum perforatum*) has the potential to significantly reduce VX-661 and ivacaftor exposure and is restricted in this study. Case-by-case exceptions for concomitant use of a moderate CYP3A inducer with VX-661/ivacaftor may be granted by the Vertex MM if it is the PI's opinion that the benefits outweigh the risks for the subject in question.

A more detailed but nonexhaustive list of study prohibitions and cautions for food and medication will be provided in the Study Reference Manual.

Table 9-1 Study Restrictions in Treatment Cohort of Study VX14-661-110

Restricted Medication/Food	Study Period
Certain fruits and fruit juices (grapefruit, grapefruit juice, Seville oranges, marmalade)	None allowed within 14 days before the first dose of the study drug through the Safety Follow-up Visit
Moderate and strong CYP3A inducers	None allowed within 14 days before the first dose of the study drug through the Safety Follow-up Visit
Commercially available CFTR modulators (e.g., ivacaftor [Kalydeco])	None allowed within 30 days before the first dose of the study drug through the Safety Follow-up Visit

CFTR: cystic fibrosis transmembrane conductance regulator; CYP: cytochrome P450.

9.4 Prior and Concomitant Medications (Treatment Cohort)

Medicinal products affected by VX-661/ivacaftor

CYP3A, P-gp, or CYP2C9 substrates

Co-administration with (oral) midazolam, a sensitive CYP3A substrate, did not affect midazolam exposure. No dose adjustment is required when co-administered with CYP3A substrates.

Based on in vitro data, ivacaftor and its M1 metabolite have the potential to inhibit P-glycoprotein (P-gp). Co-administration of VX-661/ivacaftor with digoxin, a sensitive P-gp substrate, increased digoxin exposure by 1.3-fold, consistent with weak inhibition of P-gp by ivacaftor. Administration of VX-661/ivacaftor may increase systemic exposure of medicinal products that are sensitive substrates of P-gp, which may increase or prolong their therapeutic effect and adverse reactions. Use with caution and appropriate monitoring when using concomitant digoxin or other substrates of P-gp with a narrow therapeutic index. Ivacaftor may

inhibit CYP2C9; therefore, monitoring of the international normalized ratio (INR) during co-administration of VX-661/ivacaftor with warfarin is recommended.

Information regarding all prior and concomitant medications, including the subject's CF medications, other medications, and herbal and naturopathic remedies administered at or after completion of treatment in the parent study through the Safety Follow-up Visit, if applicable, will be recorded in each subject's source documents.

- Subjects must remain on a stable CF medication (and supplement) regimen through the Safety Follow-up Visit. Stable medication regimen is defined as the current medication regimen for CF that subjects have been following for at least 28 days before Day 1. **Subjects must not initiate long-term treatment with new medication from 28 days before Day 1 through the Safety Follow-up Visit unless it is discussed and approved by the Vertex medical monitor.** Guidelines for stable medication regimens for CF are as follows:
 - Subjects who are taking daily inhaled tobramycin or other chronically inhaled antibiotics should remain on that regimen throughout the study.
 - Subjects who are on inhaled cycling antibiotics should continue on their prior schedule. The timing of the first dose of study drug should be synchronized as closely as possible to the first day of inhaled cycling antibiotics in the cycle.
 - Subjects who alternate 2 different antibiotics monthly should remain on the same schedule during the study. The timing of the first dose of study drug should be synchronized as closely as possible to the first day of 1 of the inhaled alternating antibiotics.
- There are no restrictions on the concomitant use of corticosteroids.

For subjects in the Treatment Cohort, information on bronchodilator use during the study will be collected and documented.

Subjects who are using a bronchodilator must have their spirometry assessments performed according to the guidelines provided in [Section 11.7.1](#).

9.5 Removal of Subjects (Treatment Cohort)

Subjects may withdraw from the study at any time at their own request. Subjects may be withdrawn from study drug treatment at any time at the discretion of the investigator or Vertex for safety, behavior, noncompliance with study procedures, or administrative reasons. If a subject has been withdrawn from study drug treatment, the subject will continue to be followed, provided the subject has not withdrawn consent.

Subjects who discontinue study treatment early should continue to return for study assessments at the Early Treatment Termination Visit and/or the Safety Follow-up Visit, as noted in [Section 8.1.1.3](#).

If a subject does not return for a scheduled visit, reasonable effort will be made to contact the subject. In any circumstance, reasonable effort will be made to document subject outcome. The investigator will inquire about the reason for withdrawal, request that the subject return all unused investigational product(s), request that the subject return for a Safety Follow-up Visit, if applicable (see [Section 8.1.1.2](#)), and follow up with the subject regarding any unresolved AEs.

If the subject withdraws consent for the study, no further evaluations will be performed and no additional data will be collected. Vertex may retain and continue to use any data collected before such withdrawal of consent.

9.6 Replacement of Subjects (Treatment Cohort)

Subjects who withdraw or are withdrawn during the study drug Treatment Period will not be replaced.

10 STUDY DRUG ADMINISTRATION AND MANAGEMENT (TREATMENT COHORT)

10.1 Preparation and Dispensing

Study drug may be dispensed only under the supervision of the investigator or an authorized designee and only for administration to the study subjects.

10.2 Administration

Study drug tablets will be administered orally as shown in [Table 10-1](#). Subjects in the Observational Cohort will not receive study drug.

Table 10-1 Study Drug Administration – Treatment Period

Treatment Cohort	Time	Drug(s) and Dose(s) Administered Route of Administration
VX-661/ivacaftor	AM	VX-661 100-mg/IVA 150-mg fixed-dose tablet oral
	PM	IVA 150-mg tablet oral

AM: morning; IVA: ivacaftor; PM: evening.

Treatment Cohort

Study drug should be administered within 30 minutes of starting a meal with fat-containing food, such as a standard CF high-fat, high-calorie meal or snack, according to the following guidelines:

1. Study drug should be administered q12h (\pm 2 hours). For each subject, all doses (morning and evening) of study drugs will be taken at approximately the same time each day. For example, the morning dose could be taken at 08:00 every morning and the evening dose could be taken at 20:00 every evening throughout the study.
2. On days of scheduled visits, the morning dose of study drug will be administered at the site after predose assessments have been completed. A meal or snack will be provided by the site for the morning dose of study drug.
3. If a subject's scheduled visit is to occur in the afternoon, the following guidelines must be used for administering either the morning or evening dose:
 - If the dose in the clinic will be within 6 hours of the subject's scheduled morning dose, the subject should withhold their morning dose of study drug, and the morning dose will be administered in the clinic.

- If the dose in the clinic will be more than 6 hours after the subject's scheduled morning dose, the subject should take the morning dose at home, and the evening dose will be administered in the clinic. In this event, all assessments will be collected relative to the evening dose.
4. For visits after the Day 1 Visit, subjects will be instructed to bring all used and unused study drug to the site; study drug will be dispensed at each visit, as appropriate.
 5. At the Week 96 Visit, the morning dose of study drug will NOT be administered. The last dose of study drug will be the evening dose administered the day before the Week 96 Visit.

Treatment Cohort Only:

The date, amount taken, and time of study drug administration, including whether food was taken with each dose, will be recorded for 2 days before PK sample collection and on the days of PK sample collection.

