^p Symptom-targeted physical examinations will occur at any time during the study if triggered by AEs or if deemed necessary by the investigator (**Section 11.8.3**).

^q Pregnancy tests will be performed for all female subjects of childbearing potential. All urine pregnancy tests will be performed at the site.

Table 3-1 Study VX14-661-110: Treatment Cohort

Event/Assessment ^a	Day -28 to Day -1	Treatment Period ^b						ETT Visit/ Departing Visit (Within 7 Days of Last Dose of Study Drug) ^{b,c,d,e}	Safety Follow-up Visit 28 (± 7) Days After Last Dose ^{c,d,e}
		Day 1 ^f / Returning Visit ^{b,g}	Day 15 (± 3 days)	Weeks 8, 16, 24, 36 (± 5 days)	Week 48 (± 5 days)	Weeks 60, 72, 84 (± 5 days)	Week 96 (± 5 days)		
Standard 12-lead ECG ^f		X	X	Weeks 8, 16, 24	X	Week 72	X	X	X
Vital signs ^s		X	X	X	X	X	X	X	X
Pulse oximetry ^s		X	X	X	X	X	X	X	X
Spirometry ^t		X	X	X	X	X	X	X	X
Hematology ^u		X ^v	X	X	X	X	X	X	X
Coagulation ^u		X ^v		X	X	X	X	X	X
Serum chemistry ^u		X ^v	X	X	X	X	X	X	X
Lipid panel ^u		X ^v		X	X	X	X	X	X
Vitamin levels ^u		X ^v		X	X	X	X	X	X
Urinalysis		X		X	X	X	X	X	X
PK sampling				Week 24 ^w				X	
Other events related to outcome ^x		X	X	X	X	X	X	X	X
Meal(s) or snack(s) at site ^y		X	X	X	X	X			
Study drug count			X	X	X	X	X	X	

^f All standard 12-lead ECGs will be performed before dosing and after the subject has been supine for at least 5 minutes (Section 11.8.4). At the Day 1 and 15 Visits, ECGs will be collected before dosing and at 1.5 and 4 hours after the morning dose. A window of ± 15 minutes will be allowed around the nominal times for all postdose ECG assessments. ECGs collected on Day 1 before dosing will be performed in triplicate. If study drug is not administered on the day of the visit (i.e., because of study drug interruption), only 1 ECG will be collected.

^s Vital signs and pulse oximetry will be collected before dosing and after the subject has been at rest (seated or supine) for at least 5 minutes (Sections 11.8.3 and 11.8.5).

^t Spirometry must be performed for all subjects before dosing and should be performed pre-bronchodilator (Section 11.7.1).

^u With the exception of Day 15, all blood samples will require a 4-hour fast before collection.

^v Blood samples will be collected before the first dose of study drug.

^w A single blood sample for PK will be collected within 60 minutes before dosing (Section 11.5.1).

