^x Other events related to outcome include assessments relating to pulmonary exacerbations, administration of antibiotic therapy for sinopulmonary signs or symptoms, and hospitalizations (Section 11.7.5).

^y Fat-containing food such as a standard CF high-fat, high-calorie meal or snack will be provided at the site to subjects after all predose assessments have occurred.

Table 3-1 Study VX14-661-110: Treatment Cohort

Event/Assessment ^a	Day -28 to Day -1	Treatment Period ^b						ETT Visit/ Departing Visit (Within 7 Days of Last Dose of Study Drug) ^{b,c,d,e}	Safety Follow-up Visit 28 (± 7) Days After Last Dose ^{c,d,e}
		Day 1 ^f / Returning Visit ^{b,g}	Day 15 (± 3 days)	Weeks 8, 16, 24, 36 (± 5 days)	Week 48 (± 5 days)	Weeks 60, 72, 84 (± 5 days)	Week 96 (± 5 days)		
Study drug dosing ^z		Day 1 to Week 96							
Concomitant medications		Continuous from signing of the ICF and Assent (where applicable) through the Safety Follow-up Visit							
Concomitant treatments and procedures		Continuous from signing of the ICF and Assent (where applicable) through the Safety Follow-up Visit							
AEs and SAEs ^{bb}		Continuous from signing of the ICF and Assent (where applicable) through the Safety Follow-up Visit							
AE: adverse event; CF: cystic fibrosis; CFQ-R: CF Questionnaire–Revised; ECG: electrocardiogram; ETT: Early Treatment Termination; ICF: informed consent form; PK: pharmacokinetic; SAE: serious adverse event; ██████████									

^z The study drug should be administered every 12 hours (± 2 hours) within 30 minutes of starting a meal with fat-containing food such as a standard CF high-fat, high-calorie meal or snack (Section 10.2). On days of scheduled visits, the morning dose of study drug will be administered at the site after predose assessments have been completed. The final dose of study drug will be administered the evening before the Week 96 Visit. If the Returning Visit coincides with the last Visit of the other Vertex study, the morning dose of VX-661/ivacaftor may be supplied by the other Vertex study.

^{bb} SAEs that occur after the Safety Follow-Up Visit and are considered related to study drug(s) will be reported to Vertex GPS within 24 hours as described in Section 13.1.2.2.

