 - Day 1 post-dose and Day 15 pre-/post-dose measurements will be analyzed based on nominal visit names.
 - On Day 1, the pre-dose measurements will be performed in triplicate, the average of the triplicate will be used as pre-dose measurement on Day 1. Only pre-dose measurement with nominal visit names related to the triplicate shall be used in this average.
- The visit window in the above table will still apply for the ECG data after Day 15.

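### On Day 15, an afternoon visit can tie the ECGs to the evening ivacaftor-only tablet, while the schedule and SAP time them to the morning VX-661/ivacaftor dose and pool them by nominal name

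*Protocol*

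**What the plan says.** Table 10-1 of the protocol gives VX-661 100 mg/ivacaftor 150 mg in the morning and ivacaftor 150 mg alone in the evening. VX-661 is therefore taken once a day.

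The ECG footnote to Table 3-1 sets the timing: "At the Day 1 and 15 Visits, ECGs will be collected before dosing and at 1.5 and 4 hours after the morning dose". SAP Section 11.1 (special handling for ECG) repeats this, bars mapping Day 1 and Day 15 ECGs to other visits, and adds: "Day 1 post-dose and Day 15 pre-/post-dose measurements will be analyzed based on nominal visit names".

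Protocol Section 10.2 item 3 covers afternoon visits and has two branches:

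- "If the dose in the clinic will be within 6 hours of the subject's scheduled morning dose", the morning dose is held back and given at the site.
- "If the dose in the clinic will be more than 6 hours after the subject's scheduled morning dose", then "the subject should take the morning dose at home, and the evening dose will be administered in the clinic". The item continues: "In this event, all assessments will be collected relative to the evening dose".

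The general dosing rule is in the dosing footnote to Table 3-1, "The study drug should be administered every 12 hours (± 2 hours) within 30 minutes of starting a meal", and in item 1 of Section 10.2.

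**The concern.** In the second branch the clinic tablet contains no VX-661. An ECG taken 1.5 h after that tablet meets Section 10.2 but does not meet Table 3-1 or SAP Section 11.1, neither of which carries an afternoon exception. Because the SAP works from nominal names, such a record would be summarised together with ECGs that really were taken 1.5 h after the morning dose. The Day 15 pre-dose ECG has the same problem, since it precedes the evening tablet instead of the morning one.

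ECGs are part of the primary safety endpoint (Protocol Section 7.1), and Days 1 and 15 are the only visits with scheduled post-dose ECGs. At stake is whether a line in the Day 15 ECG table means what its label says about time since VX-661.

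A second, smaller question is whether either branch keeps doses 12 ± 2 hours apart.

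**Working it through.** **Inputs.** Interval 12 ± 2 h, so 10 to 14 h (Table 3-1 dosing footnote; Section 10.2 item 1). Branch limit 6 h (Section 10.2 item 3). ECGs at 1.5 and 4 h, each ± 15 minutes (Table 3-1 ECG footnote). Tablet contents from Table 10-1.

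**The plan's own figure.** Section 10.2 illustrates the interval: "the morning dose could be taken at 08:00 every morning and the evening dose could be taken at 20:00 every evening". 20 − 8 = 12 h, inside 10 to 14 h.

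**Which visit is exposed.** The second branch needs a morning dose taken at home. At initial enrolment, Study 110 drug is first given at the Day 1 Visit, so no Study 110 morning dose can have been taken at home that day. This leaves Day 15.

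**ECG timing in the second branch.** Let g be the hours from the home morning dose to the clinic evening dose, with g > 6. Then:

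- nominal 1.5 h ECG: g + 1.5 hours after VX-661
- nominal 4 h ECG: g + 4 hours after VX-661
- pre-dose ECG: about g hours after VX-661, against about 24 h when the visit is anchored to a once-daily morning dose
- time from the evening ivacaftor tablet to the post-dose ECGs: still 1.5 and 4 h

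| g (h) | 1.5 h ECG, hours after VX-661 | 4 h ECG, hours after VX-661 | Gap to next morning dose, 24 − g | Both gaps within 10–14 h? |
|---|---|---|---|---|
| 6 (limit) | 7.5 | 10 | 18 | no |
| 8 | 9.5 | 12 | 16 | no |
| 10 | 11.5 | 14 | 14 | yes |
| 12 | 13.5 | 16 | 12 | yes |

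The ± 15 minute window moves each ECG time by 0.25 h. The documents do not define afternoon. If it means a clinic dose by 18:00 after an 08:00 morning dose (assumed), g is at most 10 and the range is 7.5 to 14 h. The 16 h figure needs a 20:00 clinic dose and an ECG at midnight.

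**Dosing interval, neighbouring doses on schedule.**

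- Second branch: the gaps are g and 24 − g. They leave 10–14 h when 6 < g < 10 and comply from g = 10 to g = 14.
- First branch, morning dose delayed by d hours: the gaps are 12 + d before and 12 − d after. At d = 2 they are 14 and 10 (compliant), at d = 3 they are 15 and 9, and at d = 6 they are 18 and 6. They leave the range for 2 < d ≤ 6.

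**The case against.** The strongest reply is that item 3 is a deliberate, specific rule for afternoon visits, worded as mandatory, and so overrides the general text. Table 3-1's dosing footnote itself refers to Section 10.2. The missed-dose rule in Section 10.5 uses the same 6-hour limit and also accepts a late morning dose followed by an evening dose at the usual time. This largely answers the interval point: sites have a rule to follow, and what remains is that the general text does not acknowledge the exception. It does not answer the ECG point, because the SAP shows no awareness of evening-anchored visits.

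The consequence is also limited. ECG output is descriptive (SAP Section 9.7.3). Threshold analyses take the worst record (SAP Section 9.1), so no extreme value is lost. The QTcF confirmation rule in Protocol Section 11.8.4 applies to any scheduled ECG. Morning dosing at the site is the default, and further ECG detail is deferred to an ECG Manual that is not available here. All of this stands and confines the problem to the Day 15 visit summaries.

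A reader might infer that these records miss a QT effect at the VX-661 peak and dilute the mean QTcF change in proportion to their number. The documents do not support that. They give no time to peak or half-life for VX-661, no concentration–QT relation and no count of afternoon visits, and the ECGs do follow an ivacaftor dose at the nominal times. Nor does the SAP say outright that the records will be labelled 1.5 and 4 h after the morning dose. That follows from combining its timing sentence with its nominal-name rule.

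**Conclusion.** The point holds for Day 15 and for the branch above 6 hours only. There the protocol's dosing section and its schedule, together with the SAP, give different reference doses for the same ECGs, and the SAP has no rule to separate them. The offset is arithmetic: post-dose ECGs at g + 1.5 and g + 4 hours after VX-661, and the pre-dose ECG at about g hours. How many visits are affected, and by how much mean QTcF would change, cannot be determined from the documents. The effect is confined to descriptive Day 15 summaries within a primary safety domain. This makes it worth correcting before lock, but it is not a threat to the safety conclusions.

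Two wider readings should be resisted. Day 1 at initial enrolment is not exposed, for the reason shown in the working. The afternoon rule does not always break the 12 ± 2 h interval: it does so for 6 < g < 10 h in one branch and for delays above 2 and up to 6 h in the other, assuming neighbouring doses stay on schedule. The interval is a matter for reconciliation, not a separate analytical defect.

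**What to change.** The sponsor should reconcile the afternoon-visit rule in Protocol Section 10.2, the ECG and dosing footnotes to Table 3-1, and the ECG handling in SAP Section 11.1. No dosing rule is proposed here.

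Before data lock, the SAP should:

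- restrict the Day 15 pre-dose and post-dose ECG summaries to records whose in-clinic dose was the VX-661/ivacaftor tablet;
- flag evening-anchored records, and records that cannot be classified, and list them separately;
- keep every record in the threshold (worst-value) counts.

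The selection must not depend on exact dose times. Section 10.2 requires these only around PK sampling, which Table 3-1 places at Week 24 and the early termination visit, not Day 15. Where they are missing, use the tablet given in clinic or the ECG clock time. Site dosing is supervised (Protocol Section 10.11) and drug administration is listed (SAP Section 9.5), so the tablet may be identifiable.

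The cost is a protocol clarification and one record-selection rule. A few ECGs would leave the Day 15 means, and some records may remain unclassifiable.
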